10.2 Efficacy Analyses

10.2.1 Primary Efficacy Variable

The primary efficacy endpoint is to assess true negative rates of the results for oral direct Factor Xa and Thrombin inhibitors of the **qualitative** visual analysis of the IVD **DOAC Dipstick** from urine samples of patients on treatment with DOACs in comparison with the **quantitative** results of DOACs obtained by **LC-MS/MS** quantification.

Statistical method: determination of a cut-off value with Logistic regression analysis, McNamar test, furthermore kappa index, accuracy, sensitivity, specificity, positive and negative predictive values with 95% confidence intervals.

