8.4 Analysis by LC-MS/MS

Urine samples will be analyzed at Laboratory Limbach by LC-MS/MS. The method is described elsewhere (23). The results are given as ng/ml. Normal range of values is 0.1 to 4.0 ng/ml (23). Normal values are interpreted as “negative”. Higher values represent “positive” results. Optionally, the upper limit of normal range may be changed to 8 ng/ml if values between 4 ng/ml and 8 ng/ml occur in more than 0.5% of patients.

Methodological reasons may lead to a repeated measurement of the urine sample diluted 1:15. Analyses will be repeated with this dilution if concentration of DOAC in urine is > 50.000 ng/ml or is expected to be above this value. The repetition is required to ensure that the concentration is in the linear range of detection range of LC-MS/MS. However, the dilution affects the normal range, which is 15-fold higher compared to samples that are

Confidentiality Statement

This document is confidential and proprietary to Sponsor and HLZ Medizinische Statistik and for restricted circulation and access only. No part of it may be transmitted, reproduced, published or used by any person/s without prior written authorization.

analysed without this dilution. For the statistical evaluation these mean of the normal range without dilution will be used.

Remark: The personal at Limbach laboratory is blinded regarding the information which DOAC the patient is taken. The personal does not have access to any information in the CRF which DAOC the patient was taking.

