8.6 Assessment of DOASENSE Control Urines

At start of study, and after every 12th examination of patient urine samples, on a DOAC Dipsticks are analysed by the visual reading and by DOASENSE Reader using DOASENSE Control Urines that are a negative control (0 ng/mL Rivaroxaban and Dabigatran, 1.5 g/L

Confidentiality Statement

This document is confidential and proprietary to Sponsor and HLZ Medizinische Statistik and for restricted circulation and access only. No part of it may be transmitted, reproduced, published or used by any person/s without prior written authorization.

creatinine and normal urine colour) and a positive control (800 ng/mL Rivaroxaban and Dabigatran and no creatinine) as described above. The results are documented on a separate page of the CRF (Quality Control to be performed at start of Study, and after every 12th Examination of Patient Urine Samples (9.5.3. Page 21, Study Protocol)) (annex5) provided by DOASENSE.

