9. EFFICACY PARAMETERS

9.1 Primary Efficacy Endpoint

The primary efficacy endpoint is to assess the performance of the results for oral direct Factor Xa and Thrombin inhibitors of the **qualitative** visual analysis of the IVD **DOAC Dipstick** from urine samples of patients on treatment with DOACs in comparison with the **quantitative** results of DOACs obtained by **LC-MS/MS** quantification.

In case the cut-off values are different for apixaban, edoxaban and rivaroxaban, as determined by LC-MS/MS this has to be taken into account for the analysis. In such case LC-MS/MS may be transformed to qualitative data for the analysis of the primary endpoint.

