10.2.2 Secondary Efficacy Variables

DOACs

- I. Comparison of the **qualitative DOAC Dipstick** results with the **qualitative** results of the **DOASENSE Reader** for DOACs

Statistical methods: determination of a cut-off value with Logistic regression analysis, McNemar test, kappa index, accuracy, sensitivity, specificity, positive and negative predictive values (with confidence intervals).

- II. Comparison of the **qualitative** results of the **DOAC Dipstick** with the **quantitative** results of **DOASENSE Reader**.

Statistical methods: determination of a cut-off value with Logistic regression analysis,

Confidentiality Statement

This document is confidential and proprietary to Sponsor and HLZ Medizinische Statistik and for restricted circulation and access only. No part of it may be transmitted, reproduced, published or used by any person/s without prior written authorization.

McNemar test, kappa index, accuracy, sensitivity, specificity, positive and negative predictive values (with confidence intervals).

III. Comparison of the **qualitative** results of the **DOASENSE Reader** with the **quantitative** results of **DOASENSE Reader**. Differences between readers have to be respected and if so, included into this analysis. Each center has an individual reader. Readers are standardized before delivery from the producer by adequate tastings, which, however do not include samples of patients under treatment. This has to be analyzed statistically in an adequate way. Number of samples may not be sufficient for all readers.

Statistical methods: determination of a cut-off value with Logistic regression analysis, McNemar test, kappa index, accuracy, sensitivity, specificity, positive and negative predictive values (with confidence intervals).

IV. Determination of the (kappa index, accuracy, sensitivity, specificity, positive and negative predictive values, cut-off value) **qualitative** results of the **DOAC Dipstick** compared to the **quantitative** results of **LC-MS/MS**.

- a. The results of rivaroxaban, apixaban and edoxaban have to be analysed separately because of different concentration ranges during therapy by LC-MS/MS. The results of the pad for factor Xa inhibitor of group B will be used to determine the statistical values. The results of the factor Xa inhibitors of group B by LC-MS/MS in urine will also be used for the statistical values.

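### The primary analysis names a fitted logistic cut-off beside the preset 4.0 ng/ml limit and does not say which one defines a positive reference result; a limit fitted to the strip's own readings is circular and can shift the error rates.

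*SAP*

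**What the plan says.** Four places in the SAP bear on the limit.

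- **10.2.1, primary variable:** "Statistical method: determination of a cut-off value with Logistic regression analysis, McNamar test", followed by kappa, accuracy, sensitivity, specificity and predictive values. Predictor scale, selection rule (50% point, Youden or other) and handling of separation are not given.
- **10.2.2, item IV (strip against LC-MS/MS):** "Determination of the (kappa index, accuracy, sensitivity, specificity, positive and negative predictive values, cut-off value", so the cut-off is an output alongside the accuracy measures. The methods for items IV and V again start with a logistic cut-off.
- **9.1:** "In case the cut-off values are different for apixaban, edoxaban and rivaroxaban, as determined by LC-MS/MS this has to be taken into account"; in that event LC-MS/MS may be made qualitative for the primary endpoint.
- **8.4:** "The results are given as ng/ml. Normal range of values is 0.1 to 4.0 ng/ml". Values in that range count as negative and higher values as positive. A data-driven option follows: "Optionally, the upper limit of normal range may be changed to 8 ng/ml".

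Section 10.1.5 makes the urine concentration by LC-MS/MS the gold standard. Section 6.2 (Determination of Sample Size) sets the aim: false-negative and false-positive proportions below 5%, with 2.5% assumed.

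**The concern.** The aim is judged on a 2×2 table, and that table needs one reference limit. The plan offers two, a preset one and one to be estimated, without ranking them.

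The estimated limit has two weaknesses. First, it is circular: the strip's readings would help define the standard by which the strip is judged. Second, the data may not carry the information. For item IV the Xa pad draws on group B, the other drug class, as well as on treated patients, and dabigatran is analysed in both groups. Concentrations may therefore form a low cluster and a much higher one. A two-parameter logistic curve must run from 0 to 1, so a few misreads at high concentration flatten it and move its 50% point.

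At stake is whether the same strip passes or fails the 5% aim. Drug-specific cut-offs could also differ only because, as item IV acknowledges, concentration ranges differ between drugs.

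**Working it through.** **Plan's own figure.** The SAP gives none for the fitted cut-off, so there is nothing to reproduce. The 440 per group is used only for group size: 440 × 0.88 = 387. Whether 440 follows from its own inputs is a separate matter.

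**Inputs from the SAP.** 2.5% errors, 5% limit and 387 per group (6.2); positive above 4.0 ng/ml (8.4).

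**Assumed, not in the SAP.** Treated patients log-normal with median 500, 2,000 or 8,000 ng/ml and log-SD 1.2; other-class patients between 0.1 and 4 ng/ml; strip either wrong in 2.5% at every concentration, or with a graded 50% threshold (slope 3 per log unit), with or without 2.5% misreads. 300 runs per setting.

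**Formulas.** logit P(strip positive) = b0 + b1·x, with x = ng/ml or log ng/ml; cut-off x = −b0/b1 (50% point). FN is the share of reference-positive samples with a negative strip. FP is the share of reference-negative samples with a positive strip.

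**Step 1: 2.5% errors at every concentration.** The strip is identical in all rows.

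| Median ng/ml | Cut-off, raw | Cut-off, log | FP at 4.0 | FP at raw | FP at log |
|---|---|---|---|---|---|
| 500 | 145 | 17 | 2.3% | 14.9% | 2.6% |
| 2,000 | 536 | 33 | 2.3% | 13.8% | 2.3% |
| 8,000 | 2,204 | 69 | 2.6% | 14.3% | 2.6% |

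FN stays at 2.3–2.6% throughout. The cut-off follows excretion. Hand check of the first row: the share of treated patients below 145 is Φ(ln(145/500)/1.2) = Φ(−1.03) = 0.151, so 387 × 0.151 = 58.5 become reference-negative, and 58.5 × 0.975 = 57.0 of them have a positive strip. FP = (387 × 0.025 + 57.0)/(387 + 58.5) = 66.7/445.5 = 15.0%.

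**Step 2: graded threshold plus 2.5% misreads.**

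| True threshold / median | Cut-off, raw | Cut-off, log | FN at 4.0 / raw / log | FP at 4.0 / raw / log |
|---|---|---|---|---|
| 50 / 500 | 157 | 26 | 6.6 / 3.0 / 5.9% | 2.5 / 13.0 / 2.6% |
| 100 / 500 | 193 | 48 | 13.5 / 4.0 / 11.2% | 2.5 / 11.6 / 2.6% |
| 200 / 500 | 296 | 119 | 26.1 / 6.6 / 17.2% | 2.5 / 10.8 / 3.2% |
| 50 / 8,000 | 2,154 | 68 | 2.5 / 2.6 / 2.5% | 2.5 / 14.3 / 2.5% |
| 200 / 8,000 | 2,181 | 70 | 2.8 / 2.5 / 2.8% | 2.5 / 14.2 / 2.5% |

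At median 8,000 a fourfold change in the strip moves the log cut-off from 68 to 70. At median 500 the log cut-off does respond to the strip, but it lies well below the true threshold.

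**Step 3: graded threshold, no misreads.** The log-scale fit recovers the strip: true 50/100/200 gives 50.5/99.5/200 at median 500 and 53/106/203 at median 2,000. At median 8,000 there is complete separation, hence no finite fit, in 291, 260 and 157 of 300 runs. Moving from 4.0 ng/ml to the fitted log cut-off lowers FN: for true 200 at median 500, from 24.8% to 8.4%.

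**Step 4: other rules.** With medians 500, 1,500 and 3,000, geometric SD 3, threshold 20 and 2.5% misreads (400 runs), raw-scale FP is 12.5–12.9%, log-scale FP 2.6–2.7%, and a Youden point (median cut-off 4.0 ng/ml) gives 2.5–2.6%.

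**The case against.** The strongest reply is that the damage needs choices the SAP does not make. Section 10.2.1 specifies neither raw ng/ml nor the 50% point, and section 19 plans ROC curves where applicable, so a Youden rule is at least as plausible. In steps 1 and 4 the log-scale and Youden cut-offs give practically the 4.0 ng/ml table. That stands: the 11–15% false-positive figures belong to one implementation.

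A reader might infer that the fitted cut-off never reflects the strip and that every error rate computed at it is an artefact. The documents do not support this. Step 3 shows the log-scale fit recovering a real threshold at moderate excretion, and a cut-off in an empty gap reclassifies almost nobody.

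A reader might also infer that the SAP orders reclassification at the fitted limit. It does not. The cut-offs in 9.1 can be read as assay limits, and 8.4 with 10.1.5 can be read as already settling the reference. What remains is that 10.2.1 and 9.1 permit the other reading and nothing excludes it.

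Nor do the documents say that the gap is empty. The range in 8.4 is a normal range, not observed data. "Analyses will be repeated with this dilution if concentration of DOAC in urine is > 50.000 ng/ml" is a conditional dilution rule. Section 8.4 also provides for values between 4 and 8 ng/ml, and the table in 10.1.5 foresees non-compliance. Few intermediate samples is therefore an assumption.

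**Conclusion.** The point holds in this form: the plan names a fitted limit first for its primary endpoint, keeps a preset limit elsewhere, and does not say which one the 5% aim is judged at. This is more than missing detail, because a limit fitted to the index test's own readings is circular on any scale.

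Under the assumed concentrations, the raw-scale 50% point takes the false-positive rate from about 2.5% to about 11–13% at median 500 with thresholds of 50–200 ng/ml, and to just under 15% elsewhere. A fitted limit lowers the false-negative rate when the strip's threshold lies within the patients' range. Where the treated cluster lies far above the threshold, the 50% point either follows excretion (with misreads) or is often inestimable (without).

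Concentration medians, spread and strip curves are invented for the check; only the direction should be relied on.

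**What to change.** In 10.2.1 and in 10.2.2 items IV and V, state that false-negative and false-positive rates, sensitivity, specificity and predictive values are computed at the LC-MS/MS limit prespecified in 8.4 only, and that no patient is reclassified at a fitted cut-off. Limit 9.1 accordingly, so that any drug-specific limit is one fixed in advance from the assay and not from strip results. The choice between 4 and 8 ng/ml within 8.4 is a separate matter.

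Keep a logistic 50% point per drug as descriptive only: strip result on log concentration, with a confidence interval, reported as not estimable under separation or with too few intermediate samples. Because misreads shift a two-parameter curve even on the log scale (step 2), free lower and upper asymptotes are preferable where the data allow. Strip-positive proportions in fixed LC-MS/MS bands, with exact intervals, are a useful optional addition.

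The cost is SAP wording and little programming. The drawback is that a single cut-off per drug may not be reportable.

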10.2.2 Secondary Efficacy Variables

DOACs

- I. Comparison of the **qualitative DOAC Dipstick** results with the **qualitative** results of the **DOASENSE Reader** for DOACs

Statistical methods: determination of a cut-off value with Logistic regression analysis, McNemar test, kappa index, accuracy, sensitivity, specificity, positive and negative predictive values (with confidence intervals).

- II. Comparison of the **qualitative** results of the **DOAC Dipstick** with the **quantitative** results of **DOASENSE Reader**.

Statistical methods: determination of a cut-off value with Logistic regression analysis,

Confidentiality Statement

This document is confidential and proprietary to Sponsor and HLZ Medizinische Statistik and for restricted circulation and access only. No part of it may be transmitted, reproduced, published or used by any person/s without prior written authorization.

McNemar test, kappa index, accuracy, sensitivity, specificity, positive and negative predictive values (with confidence intervals).

III. Comparison of the **qualitative** results of the **DOASENSE Reader** with the **quantitative** results of **DOASENSE Reader**. Differences between readers have to be respected and if so, included into this analysis. Each center has an individual reader. Readers are standardized before delivery from the producer by adequate tastings, which, however do not include samples of patients under treatment. This has to be analyzed statistically in an adequate way. Number of samples may not be sufficient for all readers.

Statistical methods: determination of a cut-off value with Logistic regression analysis, McNemar test, kappa index, accuracy, sensitivity, specificity, positive and negative predictive values (with confidence intervals).

IV. Determination of the (kappa index, accuracy, sensitivity, specificity, positive and negative predictive values, cut-off value) **qualitative** results of the **DOAC Dipstick** compared to the **quantitative** results of **LC-MS/MS**.

- a. The results of rivaroxaban, apixaban and edoxaban have to be analysed separately because of different concentration ranges during therapy by LC-MS/MS. The results of the pad for factor Xa inhibitor of group B will be used to determine the statistical values. The results of the factor Xa inhibitors of group B by LC-MS/MS in urine will also be used for the statistical values.
- b. The results of dabigatran are analysed from group B as well as from group A to determine the statistical values.

Statistical methods: determination of a cut-off value with Logistic regression analysis, McNemar test, kappa index, accuracy, sensitivity, specificity, positive and negative predictive values.

V. Comparison of the **qualitative** results of the **DOASENSE Reader** with the **quantitative** results of **LC-MS/MS**. The results of Rivaroxaban, Apixaban and Edoxaban have to be analyzed separately because of different concentration ranges

Confidentiality Statement

This document is confidential and proprietary to Sponsor and HLZ Medizinische Statistik and for restricted circulation and access only. No part of it may be transmitted, reproduced, published or used by any person/s without prior written authorization.

during therapy by LC-MS/MS.

Statistical methods: determination of a cut-off value with Logistic regression analysis, McNemar test, kappa index, accuracy, sensitivity, specificity, positive and negative predictive values.

VI. Comparison of the **quantitative** results of the **DOASENSE Reader** with the **quantitative** results of **LC-MS/MS** is performed. The results of Rivaroxaban, Apixaban and Edoxaban have to be analyzed separately because of different concentration ranges during therapy by LC-MS/MS.

Statistical method: t-test.

VII. Analysis of an **interaction of demographic data** on the results of **DOAC Dipstick**, **DOASENSE Reader** and **LC-MS/MS** (demographic data, creatinine)

Statistical method: multivariable regression analysis using SELECTION=FORWARD method

VIII. Analysis **dose, last intake and duration of treatment** with each DOAC on **qualitative** results of **DOAC Dipstick** and **DOASENSE Reader** and **quantitative** results of **LC-MS/MS**

Statistical method: multivariable regression analysis using SELECTION=FORWARD method

IX. Analysis of an **interaction of demographic data** on the results of **DOAC Dipstick**, **DOASENSE Reader** and **LC-MS/MS** (demographic data, creatinine)

Statistical method: multivariable regression analysis using SELECTION=FORWARD method

X. Analysis **dose, last intake and duration of treatment** with each DOAC on **qualitative** results of **DOAC Dipstick** and **DOASENSE Reader** and **quantitative** results of **LC-MS/MS**

Statistical method: multivariable regression analysis using SELECTION=FORWARD method

Confidentiality Statement

This document is confidential and proprietary to Sponsor and HLZ Medizinische Statistik and for restricted circulation and access only. No part of it may be transmitted, reproduced, published or used by any person/s without prior written authorization.

Creatinine

XI. Comparison of **quantitative creatinine** of Limbach (Jaffe Method) with **qualitative results of DOASENSE Reader**. A cut-off value of creatinine (g/L) needs to be determined for the colours low to normal by DOASENSE Reader. Differences between Readers needs to be analyzed.
Statistical methods: determination of a cut-off value, McNemar test, kappa index, accuracy, sensitivity, specificity, positive and negative predictive values.

XII. Comparison of results of **qualitative of creatinine by DOAC Dipstick** with **qualitative results of DOASENSE Reader**. Analysis of normal ranges of the **quantitative** results of **Urine Colour Pad of DOASENSE Reader**.
Statistical methods: McNemar test, kappa index, accuracy, sensitivity, specificity, positive and negative predictive values.

Urine Colour

XIII. Analysis of normal ranges of the **quantitative** results of **Urine Colour Pad of DOASENSE Reader**.
Statistical method: Descriptive statistic

XIV. Analysis of an interaction of the **qualitative results** of the pad **Urine Colour** on the results of the qualitative results of the pads of Factor Xa inhibitor, thrombin inhibitor and creatinine of **DOAC Dipstick** with the qualitative results **DOASENSE Reader**.

Other

Statistical method: multivariable regression analysis using SELECTION=FORWARD method

XV. Analysis of the results of **DOASENSE control urines** over time and influence on results of DOAC Dipstick and DOASENSE Reader.
Statistical method: McNemar test, kappa index, accuracy, sensitivity, specificity, positive and negative predictive values.

Confidentiality Statement

This document is confidential and proprietary to Sponsor and HLZ Medizinische Statistik and for restricted circulation and access only. No part of it may be transmitted, reproduced, published or used by any person/s without prior written authorization.

XVI. Descriptive analysis of **Drop-out** patients (case reports)
Statistical method: Descriptive statistic

XVII. Analysis of the results of the **questionnaire** and interaction on results of **DOAC Dipstick**. Center effects need to be analysed.
Statistical method: multivariable regression analysis using SELECTION=FORWARD method.
Additional statistical evaluations may be required during analysis due to the complexity of data.

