8.3 Assessment of DOAC Dipstick by DOASENSE Reader

Measurement

After the urine strip has been immersed in the urine sample for approx. 2-3 seconds according to the instructions for use, the strip is placed on the strip holder of the DOASENSE Reader after 10 minutes and the START button is pressed. The device pulls the strip holder and carries out the measurement. The result of the four pads is displayed on the screen and printed on the thermal printer. After measuring the strip, the device ejects the strip holder. The strip is removed and disposed of.

The output of DOASENSE Reader are 3-digit values reprinting the %REM values (reflectance units) of the 4 pads and printed by the Reader of the printer for each measurement that is attached with an adhesive by the study personal into the CRF. These values are then written with a ball point pen on the right part of the printed values because the printout may lose color over time.

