8.5 Analysis of Creatinine in urine

Creatinine is determined in urine by the method of Jaffe et al at Laboratory Limbach (24). Normal values are below 0.25 g/l. Values below 0.25 g/l are interpreted as "low" and higher values are interpreted as "normal". The normal range of creatinine may change upon the results of the measurement because reduced renal function with low creatinine is a contraindication for the therapy with a DOAC. If a diagnosis of renal insufficiency is documented in a patient, low creatinine value has to be interpreted as correct low. However, changes may be required upon the results of the determination of creatinine by laboratory Limbach. These decisions are made by the Steering Committee.

Data are transferred unchanged by software to an Excel file at Laboratory Limbach. This file is stored on a password secured USB flash drive and brought to the Institute for Biometry and Statistics by the Co-ordinating Investigator. [name] imports the data from Excel to SAS. Treatment of patients and data of LC-MS/MS remain blinded during this procedure. Six months after termination of the analysis of DOACs by LC-MS/MS and creatinine by Jaffe Method urine samples are discarded. This period may be changed upon request of the Sponsor of the study.

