10.1.8 Analysis Sets

Analysis set	Definition
Per protocol (PP) population	
All patients of the Full analysis population without any relevant protocol violations (major protocol deviations) and complete data for the primary efficacy variable.
 
The relevant protocol violations have to be defined prior to database closure and unblinding by a systematic data review. For this purpose, protocol violations that occurred during the trial such as violations of inclusion/exclusion criteria or forbidden concomitant medications or violation of visit time windows will be assessed as 'major' or 'minor' depending on their potential to interfere with the objectives of the trial.

Major protocol deviations and the assessment of analysis sets will be defined during last data review before data base closure. All definitions given in the Minutes of the Final Data Review will be taken into account in the analysis.

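### Items II and XI of SAP 10.2.2 fit a cut-off and report agreement in the same patients, so those figures will tend to be somewhat optimistic

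*SAP*

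**What the plan says.** - **Reader output.** SAP 8.3 states "The output of DOASENSE Reader are 3-digit values reprinting the %REM values (reflectance units) of the 4 pads". The same section says that a result for the four pads is displayed and printed. The SAP body gives no %REM limit for positive/negative or low/normal. Annex 3, the Reader guide, is listed but not shown.
- **Item II (10.2.2).** Visual Dipstick result, qualitative, against Reader, quantitative. Method: "determination of a cut-off value with Logistic regression analysis, McNemar test, kappa index, accuracy, sensitivity, specificity", then predictive values, with confidence intervals. Items I and III carry the same line, and item V carries it without the intervals.
- **Item XI (10.2.2, Creatinine).** "A cut-off value of creatinine (g/L) needs to be determined for the colours low to normal by DOASENSE Reader", followed by McNemar, kappa, accuracy, sensitivity, specificity and predictive values.
- **Creatinine limit (8.5).** The limit is 0.25 g/l, but "The normal range of creatinine may change upon the results of the measurement".
- **Readers (item III).** Each centre has its own Reader. "Differences between readers have to be respected and if so, included into this analysis". On calibration: "Readers are standardized before delivery from the producer by adequate tastings, which, however do not include samples of patients under treatment".
- **Analysis set (10.1.8).** One set only, per protocol: "All patients of the Full analysis population without any relevant protocol violations" and with complete primary data. The only validation in the SAP (section 16) checks SAS programs on about 15 patients.

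**The concern.** A cut-off chosen to separate two classes in a sample fits the chance features of that sample. Agreement, sensitivity and specificity computed in the same patients are therefore biased upward on average. Ordinary binomial intervals treat the cut-off as known, so they are also too narrow.

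Item II does this with the Reader's %REM against the visual result. Item XI does it on the reference side: the Jaffe limit is moved to suit the Reader's colours, and the Reader is then judged against the moved limit. The SAP plans no split sample, cross-validation or bootstrap correction for either.

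At stake are the published agreement between eye and Reader and the published performance of the Reader's creatinine pad. The study is framed around error rates of 2.5% and 5% (section Determination of Sample Size). On that scale one or two points would matter and a tenth of a point would not, so the size has to be worked out.

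**Working it through.** The plan gives no cut-off and no optimism figure to reproduce. The check has two parts.

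**1. Which scale is cut?**

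| Item | Variables compared | Scale of the fitted cut-off |
|---|---|---|
| I | Dipstick qualitative, Reader qualitative | none available as written |
| II | Dipstick qualitative, Reader quantitative | %REM only |
| V | Reader qualitative, LC-MS/MS quantitative | most naturally ng/ml |
| XI | Jaffe creatinine, Reader qualitative | g/L, stated |

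Only items II and XI show, on the text alone, a cut-off fitted and scored in the same patients.

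**2. How large is the optimism?**

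Inputs from the SAP: 440 per group with 12% dropout, so 440 × 0.88 = 387 evaluable per group and 774 in total; assumed error 2.5%.

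Assumptions: equal-variance normal marker in both classes; for item II, positives and negatives approximated by the two groups, 387 v 387; all per-Reader, per-drug and low-creatinine counts.

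*Item II.* Separation d = 2 × z(0.975) = 2 × 1.96 = 3.92, so the best cut-off (d/2) has error Φ(−1.96) = 2.5%. For a fitted cut-off c:
- apparent error = ½ × (share of sampled negatives above c + share of sampled positives below c)
- true error = ½ × [1 − Φ(c) + Φ(c − d)]

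Monte Carlo, 600 to 3000 replicates:

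| Setting | Cut-off rule | Apparent | True | Gap (points) |
|---|---|---|---|---|
| Pooled, 387 v 387 | logistic, p = 0.5 | 2.45% | 2.53% | 0.1 |
| Pooled, 387 v 387 | best separation | 2.2% | 2.6% | 0.4 |
| One Reader, 20 v 20 | best separation | 1.2% | 3.3% | 2.1 |
| One Reader, 15 v 15 | logistic, p = 0.5 | 1.5% | 3.1% | 1.6 |

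For one factor Xa drug (assumed 100 v 387; table row 5c lists these drugs separately) the gap is about 0.1 (logistic) or 0.8 (best separation).

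Sensitivity to the assumed error, for true errors of 2.5% to 10%: the pooled gap is 0.0 to 0.1 (logistic) or 0.4 to 0.7 (best separation). With 15 v 15 it is 1.0 to 1.6 (logistic) or 2.4 to 4.9 (best separation).

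*Item XI.* The classes are the Reader's colours and the cut is on Jaffe g/L. With Jaffe as reference, Reader sensitivity is P(Reader low | Jaffe below the cut). That is the proportion of samples below the cut that the Reader calls low. Assume AUC 0.95, so d = √2 × z(0.95) = 1.414 × 1.645 = 2.33, with a best-separation cut-off:
- 39 Reader-low of 774: 31.9% apparent v 30.4% true, gap 1.5 points
- 15 Reader-low of 774: 17.8% v 15.8%, gap 2.0 points

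The low absolute levels follow from the assumed rarity and AUC. Only the gaps matter here.

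**The case against.** A reader might infer that Reader accuracy in general is overstated, including sensitivity and specificity against LC-MS/MS, a named secondary objective. The documents do not support this.

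- The SAP treats qualitative and quantitative Reader results as separate data and compares them with each other in item III. Section 8.3 says a pad result is displayed and printed, and Annex 3 may hold a preset rule.
- The LC-MS/MS objective is item V. A cut-off there most naturally falls on the concentration scale.
- The cut-off step in item I may be copied text: item XII, also qualitative against qualitative, has none.

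A reader might also take the remark on Reader differences to mean Reader-specific cut-offs. It may equally mean a covariate. Section 10.1.9 does not stratify by centre in general, and item III concedes that samples may be too few for some Readers.

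On size, the SAP names logistic regression for the DOAC items, and a pooled logistic 50% point carries almost no optimism. For creatinine, simulated sensitivities of 90.5% v 85.7% (39 low) and 92.3% v 83.9% (15 low) suggest gaps of 4.8 and 8.4 points. Those describe Jaffe detecting the Reader's colour, not the Reader judged against Jaffe.

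All of this stands as a limit on scope and size. It does not remove the defect in items II and XI. The SAP also fixes no probability threshold and lists ROC curves among its figures, so a best-separation choice remains open. Item XI names no fitting method at all.

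**Conclusion.** The point holds for items II and XI. Each fits a cut-off and reports agreement or accuracy in the same patients, with no validated estimate, so the figures will tend to be optimistic and the intervals too narrow.

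The optimism in item II is about 0.1 to 0.4 points when pooled. It would be about 1 to 2 points with Reader-specific fitting at the SAP's 2.5% error, and more with best separation at higher error rates. In item XI it is about 1.5 to 2 points when low creatinine is rare and the cut-off is best-separation. These sizes rest on a binormal model and assumed class counts.

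Items I and V share the problem only if the Reader's qualitative result comes from a cut-off fitted in this study. The SAP body does not settle that, because it states no classification rule. A general claim that Reader accuracy is overstated goes beyond the text.

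**What to change.** Before database lock:

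1. Cite the Reader's preset %REM classification rule, with its source, and use it in items I and V.
2. Delete the cut-off step from item I.
3. In item II, classify each centre's samples with a cut-off estimated from all other centres and report agreement from those classifications. Because each centre has its own Reader, this also leaves one Reader out at a time. Otherwise, label the fitted cut-off and its agreement figures exploratory.
4. In item XI, score the Reader against the 0.25 g/l limit of 8.5, frozen before the Reader comparison. Freezing is essential, because 8.5 now lets the limit move with the results. It also calls values below 0.25 g/l both normal and low, which must be reconciled. Report any fitted g/L cut-off as exploratory.

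Cost: SAP wording, a short programming loop and slightly less favourable figures. No new data are needed.
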